**Table 1-1: Schedule of study assessments**

Period	Screening Period	Treatment Period								EW b (In-clinic)	SFU Visit c (Phone call)
Name	Screening (In-clinic)	Day 1 (In-clinic)	Day 2 (Phone call) a	Day 4 (Phone call) a	Day 6 (Phone call) a	Day 8 (Phone call) a	Day 10 (Phone call) a	Day 12 (Phone call) a	Day 14 (In-clinic)		
Visit #	1		2	3	4	5	6	7	8	9	
Day	1		2	4	6	8	10	12	14	(Final dose +7±3 days)	
Participant completes postinjection SIAQ (SIAQ POST module) j		X							X		
Study personnel collect ZLP-AI devices from each participant to send to UCB for structural/mechanical integrity assessment t m		X							X		
Drug and device accountability									X		
Record TEAEs, SAEs, ADEs, SAEs, medication errors, ISR, and device deficiencies n		X	X	X	X	X	X	X	X	X	
Blood sampling for ZLP plasma concentrations o	CCI										

ADE=adverse device effect; AE=adverse event; AI=auto-injector; βHCG=beta human chorionic gonadotropin; C-SSRS=Columbia-Suicide Severity Rating Scale; EW=early withdrawal; IMP=investigational medicinal product; ISR=injection site reaction; IXRS=interactive response technology;

MGFA=Myasthenia Gravis Foundation of America; PK=pharmacokinetic; SAE=serious adverse device event; SAE=serious adverse event; SFU=Safety

Follow-Up; SIAQ=Self-Injection Assessment Questionnaire; ZLP=zilucoplan

a Telephone visits which would be scheduled to occur on a weekend day may be skipped, and the data for the respective days (Saturday and Sunday) will be collected on the next clinic business day (Monday).

b If a study participant permanently withdraws from the study, the study participant should return to the clinic for an EW Visit as soon as possible but no later than the next scheduled in-clinic visit.

c Study participant will be required to perform a SFU telephone call 7 days (±3 days) after their final study dose of ZLP using the ZLP-AI.

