j The preinjection SIAQ (SIAQ PRE module version 2.1) will be completed preinjection at Visit 1; the postinjection SIAQ (SIAQ POST module version 2.1) will be completed directly following self-injection and no later than 30 minutes postinjection at Visit 1 and Visit 8 during the study Treatment Period.

k In accordance with the draft Food and Drug Administration Suicidal Ideation and Behavior Prospective Assessment of Occurrence in Clinical Trials

l Guidance (Food and Drug Administration, Guidance for Industry, 2012) study participants will be asked to complete the C-SSRS at study visits as specified.

m At Visits 1 and 8, the Investigator will observe the participant self-administering with the ZLP-AI device. The used ZLP-AI devices will be visually inspected by the Investigator to determine if the entire dose was completely delivered (ie, the yellow plunger that can be seen through the device window is completely depressed).

n All used AI devices will be sent to UCB for assessment of structural and mechanical integrity and damage (ie, clear evidence of damage/compromised structural integrity—not superficial, cosmetic imperfections).

o Note that ADEs, SAEs, ISRs, and medication errors can only be recorded on the 14 days that the participant is using the ZLP-AI, and device deficiencies will also be collected during those 14 days. Device deficiencies will be reported via the eCRF. In addition, sites will fill out a product quality complaint form; all product quality complaints will be investigated by UCB.

p A single PK sample will be collected **CC1**.

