**Table 3-1: Objectives and estimands/endpoints**

Objectives	Estimands/endpoints
	
 
Complete dose delivery: completeness of the delivery as confirmed by the Investigator. The entire dose of IMP should be completely delivered (ie, the yellow plunger that can be seen through the device window should be completely depressed)
 
Intercurrent event handling: 
 
No intercurrent event is defined
 
 
 
Population level summary: 
 
Proportion of participants, along with the 95% CI
 
 
 

 
Evaluate the safety and tolerability of the ZLP-AI self-administrations
 
	
Secondary endpoint:
 
 
Occurrence of SAEs, TEAEs, ADEs (serious and nonserious) from Visit 1 up to the SFU Visit
 

Other objectives	

 
Evaluate the PK of the ZLP-AI for self-administration
 
	
Other PK endpoint:
 
 
Measurement of plasma concentrations for zilucoplan and main metabolites CCI [REDACTED]
 

 
Evaluate the safety and tolerability of the ZLP-AI self-administrations
 
	
Other safety endpoints:
 
 
Occurrence of ISRs
 
Occurrence of medication errors associated with adverse reaction
 

 
Evaluate the safety of the ZLP-AI
 
	
Other safety endpoint:
 
 
Occurrence of SADEs related to the use of the ZLP-AI that would preclude continued use of the ZLP-AI for self-administration (ie, SADEs and/or SADEs leading to withdrawal from the DV0013 study)
 

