#### **Safety Follow-Up Visit**

- Visit 9: For all participants, an SFU via telephone call, 7 days ( $\pm 3$  days) after their final study dose using the ZLP-AI, will be required. Any AEs, SAEs, ADEs, or SADEs will be recorded. Participants who were enrolled into DV0013 from MG0011 will roll back into MG0011 on the next day following Visit 8 and will continue to be followed up as part of the MG0011 protocol. Participants who were enrolled following treatment with commercial ZLP treatment will continue with their prescribed treatment; for AEs occurring after the SFU telephone call and up to 40 days after the last administration, participants will be instructed to contact the site or follow the safety reporting according to the label.

The study duration for each participant will be approximately 21 days.

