#### **8.3.1 Time period and frequency for collecting AE and SAE information**

All AEs and SAEs will be collected from the signing of the ICF until the SFU Visit, at the time points specified in the SoA (Section 1.3).

In order to ensure complete safety data collection, all AEs occurring during the study (ie, after the signing of the Informed Consent form), including any pretreatment and posttreatment periods required by the protocol, must be reported in the eCRF even if no study medication was taken but specific study procedures were conducted. This includes all AEs not present prior to the initial visit and all AEs that recurred or worsened after the initial visit.

All SAEs will be recorded and reported to the Sponsor or designee within 24 hours, as indicated in Appendix 3 (Section 10.3). The Investigator will submit any updated SAE data to the Sponsor within 24 hours of it being available.

The Investigator is specifically requested to collect and report to UCB (or its representative) any SAEs (even if the Investigator is certain that they are in no way associated with the study medication) up to 40 days from the end of the study for participants who were enrolled following treatment with commercial ZLP treatment or last contact in DV0013 for participants who were enrolled from MG0011, and also to inform participants of the need to inform the Investigator of any SAE within this period. Serious AEs that the Investigator thinks may be associated with the study medication must be reported to UCB regardless of the time between the event and the end of the study.

The method of recording, evaluating, and assessing causality of AEs and SAEs and the procedures for completing and transmitting SAE reports are provided in Appendix 3 (Section 10.3).

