#### **8.3.8.1 Time period for detecting ADEs and device deficiencies**

Adverse device effects and device deficiencies will be detected, documented, and reported during all periods of the study in which the device is used.

If the Investigator learns of any ADEs or device deficiencies at any time after a participant has been discharged from the study, and such event(s) is considered reasonably related to a device provided for the study, the Investigator will promptly notify the Sponsor.

The method of documenting ADEs and device deficiencies is provided in Appendix 7 (Section 10.7).

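### A schedule footnote closes recording of device effects and injection site reactions at the end of device use, while the secondary safety endpoint and the follow-up call run on to the SFU Visit

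*Protocol*

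**What the plan says.** The restriction stands in the footnotes to Protocol Table 1-1 (Section 1.3): "Note that ADEs, SAEs, ISRs, and medication errors can only be recorded on the 14 days that the participant is using the ZLP-AI". The same footnote confines device deficiencies to those 14 days.

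Other parts of the plan set a longer window:

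- Protocol Table 3-1, secondary safety endpoint: "Occurrence of SAEs, TEAEs, ADEs (serious and nonserious) from Visit 1 up to the SFU Visit". The synopsis and SAP Table 1–1 give the same window.
- Protocol 4.1, on the SFU call (Visit 9): "Any AEs, SAEs, ADEs, or SADEs will be recorded". The synopsis and SAP 1.2 agree.
- Protocol 8.3.1: "All AEs and SAEs will be collected from the signing of the ICF until the SFU Visit". The same sentence sends sites to the schedule for the time points.
- SAP 4.5.3 identifies ISRs from coded AEs that start between the first ZLP-AI injection and safety follow-up.

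One section of the protocol body lies nearer to the footnote. Section 8.3.8.1 says: "Adverse device effects and device deficiencies will be detected, documented, and reported during all periods of the study in which the device is used". It then adds a duty to notify the sponsor of related events that the investigator learns of after the participant has been discharged from the study.

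**The concern.** Safe use of the auto-injector is in the study title, and ADEs are a named part of a secondary endpoint. A reaction to one of the last injections may first show, or first be reported, after Day 14. The SFU call is the one scheduled contact at which a participant who completes treatment could report it.

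Protocol Section 8 makes adherence to the schedule mandatory, so a site has good reason to follow the footnote. Another site may as reasonably follow Section 4.1. The two would then record ADEs and ISRs over different periods, and the pooled counts would not match the window that the endpoint names. This is a matter of data collection. The SAP can define the analysis window as it likes, but it cannot restore a device attribution that was never entered. The list of changes from the protocol in SAP 4.8 does not mention the point.

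**Working it through.** **Timing inputs.** Fourteen daily self-administrations on Days 1 to 14 (Protocol 6.1). SFU call at "Final dose +7±3 days" (Table 1-1). Study duration of about 21 days per participant (Protocol 4.1).

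**The plan's own figure.** 14 treatment days + 7 days to the call = 21 days, as stated.

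**Share of the endpoint window closed by the footnote, read literally.** Let d be the number of days from the Day 14 injection to the call. The window from Visit 1 to SFU has 14 + d days, and the footnote closes the last d of them.

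| d | SFU day | Closed share d / (14 + d) |
|---|---|---|
| 4 | 18 | 4/18 = 22% |
| 7 | 21 | 7/21 = 33% |
| 10 | 24 | 10/24 = 42% |

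For the Day 14 injection, the footnote leaves only the rest of that day for recording an ADE or ISR. The endpoint window gives 4 to 10 days.

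**Does a softer reading remove the conflict?** The footnote might be meant to limit the days on which an event can start, not the days on which it can be written down. An event that began by Day 14 and was reported at the SFU call would then be recordable. An ADE that begins on Day 15 because of the Day 14 injection would still be shut out, although Table 3-1 counts it. The conflict is narrower but remains.

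**Does Section 8.3.8.1 settle it?** It covers periods of device use, and then events learned of after discharge from the study. Day 15 to the SFU call is neither: the device is no longer in use, and the participant has not yet completed the study.

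**Where do events after Day 14 go?** MG0011 participants return to MG0011 on the day after Visit 8, and the others return to commercial supply (Protocol 4.1 and 6.8). SAP 4.5.2 sends AEs after that return to MG0011 or to spontaneous reporting, unless there is clear evidence of a link with the ZLP-AI, in which case DV0013 captures them. The late events that the SAP reserves for DV0013 are thus the device-related ones that the footnote would not let a site record as such.

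**Which event types are affected?** ADEs and ISRs are unambiguous. The footnote also lists SAEs, but this may stand for SADEs, since the abbreviation list under the table expands SAE as a serious adverse device event in one place. If SAEs are truly meant, the footnote also contradicts Section 8.3.1. The conclusion does not rest on this.

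**The case against.** The strongest reply is that late events have another route into the database. The footnote does not list AEs or TEAEs, and Protocol 8.3.1 requires all AEs, including those in post-treatment periods, to be reported in the eCRF. An ADE is by definition an AE related to device use (Protocol 9.4.2 and 10.7.1). SAP 4.5.2.1 derives ADEs from the device-relationship item on the AE page, and SAP 4.5.3 derives ISRs from coded AE terms. If a site enters the late event as an AE and completes that item, the endpoint can be produced. This stands. A reader might infer that the ADE part of the endpoint cannot be delivered or that late reactions must go unrecorded; the documents do not support that.

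A second reply is that the footnote has a sensible purpose. From Day 15 participants inject with their earlier presentation again, so a new injection-site event may not come from the ZLP-AI. This also stands. It argues for an attribution rule, however, and not for a stop on recording that the endpoint contradicts.

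A reader might also infer that the schedule leaves the SFU cell empty in the row labelled "Record TEAEs, SAEs, ADEs, SAEs, medication errors, ISR, and device deficiencies". That cannot be shown. The row has eleven data cells, with nine marks in cells 2 to 10. On that page of the text read from PDF, the entries for Visit 9 and its timing stand in the tenth cell, together with the ninth mark. On the table's first page Visit 9 stands in the eleventh. The columns are displaced, so the ninth mark may belong to Early Withdrawal or to SFU. The footnote conflict is the same either way.

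**Conclusion.** The concern holds as a contradiction inside the protocol, carried into the SAP. The footnote and the endpoint give two different windows for ADEs, the footnote and SAP 4.5.3 give two for ISRs, and Section 8.3.8.1 leaves Day 15 to the SFU call unassigned. On the literal reading, about one third of the endpoint window is closed to recording events as ADEs or ISRs. That figure assumes a final injection on Day 14 and is a share of days, not of events; the documents give no rate of late device events from which to estimate a number missed.

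The consequence is a risk of missed or inconsistent device attribution between sites. It is not a certain loss of safety data. A correction is warranted because the ambiguity touches a named secondary endpoint and little is needed to remove it.

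**What to change.** 1. Reword the Table 1-1 footnote so that only device deficiencies and medication errors are tied to the 14 days of device use. State that ADEs, SADEs and ISRs attributed to a ZLP-AI injection are recorded through the SFU call.
2. Align Protocol 8.3.8.1 with this, so that the time from the last injection to the SFU call is covered explicitly.
3. For any event that starts after Day 14, have the investigator record whether it relates to the ZLP-AI or to the presentation resumed afterwards.
4. Settle whether the footnote means SAEs or SADEs, and check in the typeset table that the event-recording row is marked at SFU.
5. If data are already collected, state in the CSR which recording window sites applied, and read the ADE and ISR counts in that light.

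The cost is a few sentences of protocol wording, a brief instruction to sites and, if it is not already available, AE entry with an attribution item at the SFU visit in the eCRF. The call already takes place, so no contact with participants is added.

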## 2 INTRODUCTION

### 2.1 Study rationale

Myasthenia gravis is a serious, sometimes life-threatening, debilitating condition associated with numerous symptoms including muscular weakness and fatigue. Some patients can manage their symptoms with oral medications such as oral acetylcholinesterase inhibitors, corticosteroids, or nonsteroidal immunosuppressants. In addition, intravenous immunoglobulin G and plasma exchange treatment could be utilized. For those whose symptoms are not well managed by these medications, a potential alternative is long-term treatment with approved IV C5 inhibitors (eg, eculizumab or ravulizumab) which have proven effective at treating MG symptoms.

Zilucoplan (RA101495; ZLP) was recently approved in the US and EU and is currently available as a PFS for sc injection. The PFS reduces drug administration burden and can be used by patients with difficult venous access or who are in underserved or rural populations where economic access to IV infusions is prohibitive. However, it is expected that there will be a need to have different treatment administration options available for the administration of ZLP and that individuals may prefer to have the option to administer their ZLP medication using an AI. The AI device may improve the handling of the drug administration and improve compliance. DV0013 will, therefore evaluate the safe and effective self-administration with the ZLP-AI as an administration option.

### 2.2 Background

Myasthenia gravis is a rare complement-mediated autoimmune disease characterized by the production of autoantibodies targeting proteins that are critical for the normal transmission of neurotransmitter signals from nerves to muscles. The prevalence of MG globally is estimated to be 12.4 (range 10.6 to 14.5) per 100,000 persons (Salari et al, 2021), hence, MG affects up to approximately 760,000 people worldwide. Myasthenia gravis most commonly affects young adult women (under 40) and older men (over 60), but it can occur at any age. Epidemiological studies reveal an increasing prevalence over the past 50 years, due in part to an increase in the frequency of diagnosis in the elderly (Sanders et al, 2016). As the population has aged, the average age at onset has increased correspondingly. In 15% of patients with MG, symptoms remain confined to the ocular muscles. In approximately 85% of patients, MG progresses beyond the ocular muscles to affect multiple muscle groups throughout the body, a condition that is typically referred to as gMG (Gilhus, 2016).

Patients with gMG present with muscle weakness that characteristically becomes more severe with repeated use and recovers with rest. Symptoms are typically at their mildest in the morning, when overnight inactivity enables replenishment of acetylcholine levels in presynaptic motor nerve terminals, and worsen during the course of the day. Muscle weakness can be localized to specific muscles, but often progresses to more diffuse muscle weakness (Gilhus, 2016; Gilhus and Verschuuren, 2015; Chamanza et al, 2010). Generalized MG symptoms can become life-threatening when muscle weakness involves the diaphragm and intercostal muscles in the chest wall that are responsible for breathing. The most dangerous complication of gMG, known as myasthenic crisis, requires hospitalization, intubation, and mechanical ventilation. Approximately 15% to 20% of patients with gMG will experience a myasthenic crisis within 2 years of diagnosis (Ramizuddin, 2014).

Zilucoplan is a 15-amino acid macrocyclic peptide complement inhibitor designed for the treatment of conditions in which inappropriate activation of C5 has been demonstrated to play a role. Zilucoplan binds to C5 with high affinity and prevents its cleavage by C5 convertases into the cleavage products C5a and C5b. Inhibition of C5 cleavage prevents the downstream assembly and cytolytic activity of the membrane attack complex. Pharmacologically, ZLP has demonstrated dose-dependent inhibition of C5a and C5b formation following activation of classical or alternative complement pathways, as well as inhibition of red blood cell lysis in the serum/plasma from various species.

The clinical efficacy of ZLP in gMG has been shown in a Phase 2 study, MG0009 (previously RA101495-02.201), and in a Phase 3 study, MG0010 (previously RA101495-02.301) (Howard et al, 2023). In addition, ZLP has shown a favorable safety and tolerability profile across all completed studies. Further details are provided in the ZLP Investigator's Brochure (IB).

### 2.3 Benefit/risk assessment

The primary risk associated with C5 inhibitors as a class is increased susceptibility to infections with encapsulated bacteria, such as *Neisseria* spp. Specifically, this risk is related to suppression of the innate immune response and subsequent infections, particularly meningococcal infections. It is well established that inhibition of C5 and the terminal complement pathway increases the susceptibility to *Neisseria* spp. infections. Given the known increased risk of meningococcal infection (*Neisseria meningitidis*) associated with inhibition or inherited deficiency of C5, participants in this study will be required to have documentation of *N. meningitidis* vaccination at least 14 days prior to IMP administration, if not vaccinated within 3 years prior to the start of treatment. Participants must be vaccinated with a quadrivalent vaccine (where available and in accordance with local standard of care) and serogroup B vaccine against meningococcal infections (*N. meningitidis*), and booster vaccinations should be administered in accordance with local standard of care. In addition, while on ZLP, study participants must be monitored closely for signs and symptoms of *N. meningitidis* infection, including self-monitoring and caregiver monitoring based on detailed instructions about signs and symptoms of possible meningococcal infections. To date, no meningococcal infections have been identified with ZLP treatment in clinical studies, as the risk of *Neisseria* infection is well-managed by appropriate prophylactic vaccination.

Together, the nonclinical and clinical data generated by investigations with ZLP support the use of ZLP in patients with gMG. While both benefits and risks may be associated with the administration of any investigational medicine, to date, ZLP has shown good tolerability and a favorable safety profile across studies in healthy adult study participants and adult study participants with CCI, immune-mediated necrotizing myopathy, gMG, paroxysmal nocturnal hemoglobinuria, coronavirus Disease 2019 (COVID-19)-associated respiratory syndrome, and amyotrophic lateral sclerosis. The bioequivalence of the AI device is under investigation in DV0012; however the AI device may improve the handling of the drug administration and improve compliance.

Considering the potential benefits, risks, and mitigation measures in place, UCB considers the overall benefit/risk to be favorable for participants in this study.

More detailed information about the known and expected benefits and risks and reasonably expected adverse events of ZLP may be found in the IB.

### 3 OBJECTIVES AND ENDPOINTS

**Table 3-1: Objectives and estimands/endpoints**

Objectives	Estimands/endpoints
Primary	

 
To evaluate the effectiveness of ZLP-AI self-administration
 
	
Primary estimand
 
 
Treatment: Zilucoplan
 
Target Population: Participants aged <math>\geq 18</math> years with gMG, already treated with zilucoplan (currently participating in MG0011 or treated with commercial zilucoplan)
 
Endpoint: Effective self-administrations of zilucoplan using the ZLP-AI from Visit 1 to Visit 8. Effective self-administration is defined as: 
 
Complete dose delivery: completeness of the delivery as confirmed by the Investigator. The entire dose of IMP should be completely delivered (ie, the yellow plunger that can be seen through the device window should be completely depressed)
 
 
 
Intercurrent event: 
 
No intercurrent event is defined
 
 
 
Population level summary: 
 
Proportion of effective self-administrations overall (total number of self-administrations from Visit 1 to Visit 8), along with the 95% CI
 
 
 

Secondary	

 
To evaluate the effectiveness of ZLP-AI self-administration using additional effectiveness endpoints
 
	
Secondary estimands
 
 
Treatment: Zilucoplan
 
Target Population: Participants aged <math>\geq 18</math> years with gMG, already treated with zilucoplan (currently participating in MG0011 or treated with commercial zilucoplan)
 
Endpoints: 
 
Effective self-administration of zilucoplan using ZLP-AI at Visit 8. Effective self-administration is defined as complete dose delivery.
 
Effective self-administration of zilucoplan using ZLP-AI at Visit 1. Effective self-administration is defined as complete dose delivery
 
 
 

